**Table 2: ISSHP classification of hypertensive disorders in pregnancy**

Classification of the HDP.

	Comments
Pre-existing (chronic) hypertension	This is defined as hypertension that was present either pre-pregnancy or that develops at <20  weeks gestation
• With comorbid condition(s)	Comorbid conditions (e.g., pre-gestational type I or II diabetes mellitus or kidney disease) warrant tighter BP control outside of pregnancy because of their association with heightened cardiovascular risk
• With evidence of preeclampsia	This is also known as 'superimposed preeclampsia' and is defined by the development of one or more of the following at ≥ 20 weeks: 
 
• Resistant hypertension, or
 
• New or worsening proteinuria, or
 
• One/more adverse condition(s) or
 
• One/more severe complication(s)
 
 Severe preeclampsia is defined as preeclampsia with one or more severe complication(s)
Gestational hypertension	This is defined as hypertension that develops for the first time at ≥ 20  weeks' gestation
• With comorbid condition(s)	Comorbid conditions (e.g., pregestational type I or II diabetes mellitus or kidney disease) warrant tighter BP control outside of pregnancy because of their association with heightened cardiovascular risk
• With evidence of preeclampsia	Evidence of preeclampsia may appear many weeks after the onset of gestational hypertension. Preeclampsia is defined by gestational hypertension and one or more of the following: 
 
• New proteinuria, or
 
• One/more adverse condition(s) or
 
• One/more severe complication(s)
 
 Severe preeclampsia is defined as preeclampsia with one or more severe complication(s)
Preeclampsia	Preeclampsia may arise de novo . It is defined by gestational hypertension and one or more of the following: 
 
• New proteinuria, or
 
• One/more adverse condition(s) or
 
• One/more severe complication(s)
 
 Severe preeclampsia is defined as preeclampsia with one or more severe complications v
'Other hypertensive effects'	
Transient hypertensive effect	Elevated BP may be due to environmental stimuli or the pain of labour, for example
White coat hypertensive effect	BP that is elevated in the office (sBP ≥ 140 mmHg or dBP ≥ 90 mmHg) but is consistently normal outside of the office (<135/85 mmHg) by ABPM or HBPM
Masked hypertensive effect	BP that is consistently normal in the office (sBP < 140 mmHg or dBP < 90 mmHg) but is elevated outside of the office (≥ 135/85 mmHg) by ABPM or repeated HBPM

ABPM, ambulatory BP monitoring; BP, blood pressure; HBPM, home BP monitoring.

v These may occur in women whose BP is elevated at <20^0 or ≥20^0 weeks who are suspected of having pre-existing or gestational hypertension/preeclampsia, respectively.

**Table 3: ISSHP classification of adverse conditions and severe complications of preeclampsia**

Adverse conditions and severe complications of preeclampsia.

Organ system affected	Adverse conditions (that increase the risk of severe complications)	Severe complications (that warrant delivery)
CNS	
 
○ Headache/visual symptoms
 
	
 
○ Eclampsia
 
○ PRES
 
○ Cortical blindness or retinal detachment
 
○ Glasgow coma scale < 13
 
○ Stroke, TIA, or RIND
 

Cardiorespiratory	
 
○ Chest pain/dyspnoea
 
○ Oxygen saturation < 97%
 
	
 
○ Uncontrolled severe hypertension (over a period of 12hr despite use of three antihypertensive agents),
 
○ Oxygen saturation < 90%, need for ≥ 50% oxygen for > 1hr, intubation (other than for Caesarean section), pulmonary oedema
 
○ Positive inotropic support
 
○ Myocardial ischaemia or infarction
 

Haematological	
 
○ Elevated WBC count
 
○ Elevated INR or aPTT
 
○ Low platelet count
 
	
 
○ Platelet count < 50x10^9/L
 
○ Transfusion of any blood product
 

Renal	
 
○ Elevated serum creatinine
 
○ Elevated serum uric acid
 
	
 
○ Acute kidney injury (creatinine > 150 μM with no prior renal disease)
 
○ New indication for dialysis
 

Hepatic	
 
○ Nausea or vomiting
 
○ RUQ or epigastric pain
 
○ Elevated serum AST, ALT, LDH, or bilirubin
 
○ Low plasma albumin
 
	
 
○ Hepatic dysfunction (INR > 2 in absence of DIC or warfarin)
 
○ Hepatic haematoma or rupture
 

Feto-placental	
 
○ Non-reassuring FHR
 
○ IUGR
 
○ Oligohydramnios
 
○ Absent or reversed end-diastolic flow by Doppler velocimetry
 
	
 
○ Abruption with evidence of maternal or fetal compromise
 
○ Reverse ductus venosus A wave
 
○ Stillbirth
 

AST, aspartate aminotransferase; ALT, alanine aminotransferase; DIC, disseminated intravascular coagulation; FHR, fetal heart rate; LDH, lactate dehydrogenase; PRES, posterior reversible leukoencephalopathy syndrome; RIND, reversible neurological deficit < 48hr; RUQ, right upper quadrant; TIA, transient ischaemic attack.

A number of patients seen at Tygerberg Hospital only book after a gestational age of 20 weeks. The ISSHP classification systems does not have a class for these patients. We will classify these patients according to the classification of Davey and MacGillivray.

**Unclassified proteinuric hypertension:**

Hypertension and proteinuria diagnosed in a patient who is seen for the first time after 20 weeks of gestation.

We will then contact these patients after 6 weeks after the expected due date to determine whether their blood pressure has normalized or not and will then retrospectively reclassify them as either as pre-eclampsia or chronic hypertension with superimposed pre-eclampsia.

## 5.2 Inclusion criteria

A diagnosis of pre-eclampsia, gestational hypertension with evidence of preeclampsia, preexisting hypertension with evidence of pre-eclampsia or unclassified proteinuric hypertension has been made by the attending clinician who believes the patient and fetus would benefit from expectant management.

**AND** all of the following is present:

- Gestational age between 26 + 0 weeks and 31 + 6 weeks
- Estimated fetal weight by ultrasound between 500gm and 1800 gm (if gestation is not certain)
- Singleton pregnancy
- The managing clinicians have made the assessment to proceed with expectant management and that delivery is not expected within 48 hours
- The managing clinician and neonatologist believe that the fetus could potentially be delivered in a viable condition

**ALSO:**

- The mother must be able to understand the information provided, with the use of an interpreter if needed, and must be able to give informed consent
- Patient will be admitted to hospital for expectant management and standardised care

## 5.3 Exclusion criteria

- Patient is unable or unwilling to give consent
- Established fetal compromise that necessitates delivery. This will be decided by the clinical team before expectant management is offered to the patient.

- Suspicions of a major fetal anomaly or malformation. A major fetal anomaly is defined as anomalies or malformations that create significant medical problems for the patient or that require specific surgical or medical management. Major anomalies or malformations are not considered a variation of the normal spectrum.
- The presence of any of the following at presentation:
  - Eclampsia defined as the new onset of grand mal seizure activity and/or an unexplained coma during pregnancy with signs or symptoms of pre-eclampsia.
  - Severe hypertension defined as a systolic blood pressure greater than or equal to 160 mmHg or diastolic blood pressure greater than or equal to 110 mmHg that cannot be controlled with antihypertensive medication within 48 hours of admission.
  - Cerebrovascular event defined as an ischaemic or haemorrhagic stroke associated with clinical symptoms and definitive signs on imaging.
  - Posterior reversible encephalopathy syndrome (PRES) associated with pre-eclampsia defined on imaging as reversible vasogenic oedema, usually in the occipital or parietal lobes.
  - Severe renal impairment with a creatinine level of greater or equal to 125 µmol/l or a need for dialysis.
  - Signs of left ventricular failure which include pulmonary oedema requiring treatment or oxygen saturations of less than 90% caused by left sided heart failure.
  - Disseminated intravascular coagulation defined as an INR greater than 2
  - Platelet count at presentation less than  $50 \times 10^9$  (platelet aggregation excluded)
  - Haemolysis, elevated liver enzymes and low platelets (HELLP) syndrome defined as a platelet count less than  $100 \times 10^9/L$ , aspartate aminotransferase greater than 60 µ/L, and haemolysis as demonstrated by lactate dehydrogenase > 600 µ/L or haemolysis on a peripheral blood smear.
  - Liver transaminases greater than or equal to 500IU/L
  - Liver haematoma or rupture
  - Fetal distress on cardiotocography
  - Severe ascites on ultrasound as defined by the sonographer
- Contra-indications for expectant management of pre-eclampsia
- Current use of metformin or a clinical indication for the use of metformin
- Contraindications to the use of metformin
  - Renal disease or dysfunction, suggested by a creatinine level greater than 124µmol/L
  - Known hypersensitivity to metformin
  - Acute or chronic metabolic acidosis, including diabetic ketoacidosis
- Current use of a drug that may be affected by metformin
  - Glyburide

- Furosemide
- Cationic drugs (amiloride, digoxin, morphine, procainamide, quinidine, quinine, rantidine, triamterene, trimethoprim and vancomycin)

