### **2.5.2.5 Drug interactions**

Furosemide—Pharmacokinetic parameters of both compounds are affected by coadministration. Furosemide increases the metformin plasma and blood Cmax by 22% and blood AUC by 15%, without any significant change in metformin renal clearance.

Nifedipine—A single-dose, metformin-nifedipine drug interaction study in normal healthy volunteers demonstrated that coadministration of nifedipine increased plasma metformin Cmax and AUC by 20% and 9%, respectively, and increased the amount excreted in the urine. Tmax and half-life were unaffected. Nifedipine appears to enhance the absorption of metformin. Metformin had minimal effects on nifedipine.

Cationic drugs—Cationic drugs (e.g., amiloride, digoxin, morphine, procainamide, quinidine, quinine, ranitidine, triamterene, trimethoprim, or vancomycin) that are eliminated by renal tubular secretion theoretically have the potential for interaction with metformin by competing for common renal tubular transport systems. Such interaction between metformin and oral cimetidine have been observed in normal healthy volunteers in both single- and multiple-dose, metformin-cimetidine drug interaction studies, with a 60% increase in peak metformin plasma and whole blood concentrations and a 40% increase in plasma and whole blood metformin AUC. There was no change in elimination half-life in the single-dose study. Metformin had no effect on cimetidine pharmacokinetics.

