### **2.5.2.7 Pharmacokinetics**

The absolute bioavailability of metformin 500mg tablet given under fasting conditions is approximately 50% to 60%. Studies using single oral doses of metformin 500mg to 1500mg, and 850 to 2550mg, indicate that there is a lack of dose proportionality with increasing doses, which is due to decreased absorption rather than an alteration in elimination.

Food decreases the extent of, and slightly delays the absorption of metformin, as shown by approximately a 40% lower mean peak plasma concentration (Cmax), a 25% lower area under the plasma concentration versus time curve (AUC), and a 35-minute prolongation of time to peak plasma concentration (Tmax) following administration of a single 850mg tablet of metformin. Cmax is achieved with a median value of 7 hours and a range of 4 to 8 hours.

After repeated administration metformin did not accumulate in plasma.

Metformin is negligibly bound to plasma proteins. Metformin partitions into erythrocytes, most likely as a function of time. At usual clinical doses and dosing steady state plasma concentrations of metformin are reached within 24 to 48 hours and are usually <1  $\mu$ g/mL. During controlled clinical trials, maximum plasma levels did not exceed 5  $\mu$ g/mL, even at maximum doses.

Metformin is excreted unchanged in the urine and does not undergo hepatic metabolism or biliary excretion. Renal clearance is approximately 3.5 times greater than creatinine clearance, which indicates that tubular secretion is the major route of metformin elimination. Following oral administration, approximately 90% of the absorbed drug is eliminated via the renal route within the first 24 hours, with a plasma elimination half-life of approximately 6.2 hours. In blood, the

elimination half-life is approximately 17.6 hours, suggesting that the erythrocyte mass may be a compartment of distribution.

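### The cationic-drug exclusion in Protocol 5.3 does not name cimetidine, the one cationic drug with an observed metformin interaction in the protocol, and its lead-in points away from it

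*Protocol*

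**What the plan says.** Protocol 5.3 ends with an exclusion for current use of drugs on which metformin may have an effect. Under it stand glyburide, furosemide and "Cationic drugs (amiloride, digoxin, morphine, procainamide, quinidine, quinine, rantidine, triamterene, trimethoprim and vancomycin".

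The background for this is Protocol 2.5.2.5. It introduces the class with "Cationic drugs (e.g., amiloride, digoxin, morphine, procainamide, quinidine, quinine, ranitidine, triamterene, trimethoprim, or vancomycin" and says that these drugs "theoretically have the potential for interaction with metformin by competing for common renal tubular transport systems". It then turns to a drug outside the bracket: "Such interaction between metformin and oral cimetidine have been observed in normal healthy volunteers", in single-dose and multiple-dose studies, "with a 60% increase in peak metformin plasma and whole blood concentrations and a 40% increase in plasma and whole blood metformin AUC". It adds that metformin did not alter the pharmacokinetics of cimetidine.

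Protocol 2.5.2.7 says that "tubular secretion is the major route of metformin elimination". Cimetidine appears in no other section of either document. SAP item 20 refers to the protocol for eligibility and adds no drug restriction.

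**The concern.** The protocol chose to keep out women on drugs whose interaction with metformin is only a theoretical possibility. By that standard, the drug in the same class with a measured interaction has the stronger claim to be named. The bracket in 5.3 reproduces the ten examples from 2.5.2.5 and stops before the cimetidine sentence. Without the e.g., it reads more like a complete list than a set of examples.

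What is at stake is consistent screening on a safety criterion. A woman on ranitidine is plainly excluded. A woman on cimetidine is excluded or admitted according to how the screener reads the bullet. If she is admitted and allocated metformin, she takes up to 3 g daily with a drug that raised metformin exposure in volunteers, and the elimination route that 2.5.2.5 links to this interaction is the main one.

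**Working it through.** The plan states no figure to reproduce. The check sets the two sections side by side and compares the exposure figures in 2.5.2.5.

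**Count.** Cationic drugs named in 2.5.2.5: ten after the e.g., plus cimetidine, so 10 + 1 = 11. Named in 5.3: 10, the same ten. The one left out is the only one of the eleven with measured figures.

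**Size of the reported interactions.** All figures are from 2.5.2.5: cimetidine as quoted above; furosemide peak +22% and "blood AUC by 15%, without any significant change in metformin renal clearance"; nifedipine peak "and AUC by 20% and 9%, respectively, and increased the amount excreted in the urine".

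| Drug | Metformin peak | Metformin AUC | Effect of metformin on the drug | Named in 5.3 |
|---|---|---|---|---|
| Cimetidine | +60% | +40% | none | no |
| Furosemide | +22% | +15% | yes, both drugs are altered | yes |
| Nifedipine | +20% | +9% | minimal | no |
| The ten listed drugs | not given | not given | not given | yes |

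- Ratio of rises, cimetidine to furosemide: peak 60/22 = 2.7; AUC 40/15 = 2.7.
- Ratio of exposures, cimetidine to furosemide: peak 1.60/1.22 = 1.31; AUC 1.40/1.15 = 1.22.
- Ratio of exposures, cimetidine to nifedipine: peak 1.60/1.20 = 1.33; AUC 1.40/1.09 = 1.28.

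These ratios compare separate interaction studies. They rank the reported figures and say nothing about clinical effect.

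**Does the lead-in explain the list?** The fourth column tests this. For the three drugs with measured data, it does: furosemide is altered by metformin and is listed, while cimetidine and nifedipine are not materially altered and are not listed. For the ten cationic drugs, it does not. Section 2.5.2.5 gives no evidence that metformin alters any of them; its ground for the class is competition for renal tubular transport. Cimetidine is the case in which it says such an interaction was seen. The list therefore mixes two grounds, and the lead-in states only one.

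**Number of women.** The documents do not say how many women in this population take cimetidine. Purely as an assumption, use of 0% to 2% would mean 0 to 0.02 × 150 = 3 of the 150 women.

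**The case against.** The strongest case against the point is the wording of the criterion. It concerns drugs that metformin may act on, and 2.5.2.5 says that metformin does not act on cimetidine. Read literally, cimetidine falls outside the criterion, and its absence is consistent with the text. This stands in part: adding cimetidine under an unchanged lead-in would contradict the protocol's own background section. It does not remove the point, because the same lead-in does not account for the ten drugs that are listed.

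Second, the bullet names a class, and 2.5.2.5 treats cimetidine as showing that class's interaction. A screener who reads the two sections together would exclude it. That is a fair reading, and treating the bracket as closed is only an interpretation. The two readings pull in opposite directions, which is the reason to settle the wording.

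Third, a reader might infer that 5.3 was meant to select drugs by how much they raise metformin exposure, so that omitting the largest is a plain error. The documents do not say so. Nifedipine raises the metformin peak almost as much as furosemide does and is permitted.

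Fourth, no harm is shown. Section 2.5.2.5 reports no change in metformin half-life in the single-dose study. Section 2.5.2.7 reports low usual plasma levels and no accumulation, though not for use with cimetidine. Women enter under a creatinine limit (5.3), are inpatients with twice-weekly renal tests (7.3.1), and can have the dose lowered for side effects (4.3, 7.2.5). All of this stands and limits the weight of the point.

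**Conclusion.** The point holds as a minor correction to a safety-eligibility criterion. Section 5.3 names ten cationic drugs with a theoretical interaction and does not name the one with an observed interaction, and the lead-in does not match the ground on which the class is listed. The size is one drug out of eleven, with reported rises in metformin exposure about 2.7 times those for furosemide.

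A reader might go further and infer that the trial knowingly admits women to a dangerous combination. The documents do not support that. They give no harmful concentration and do not link cimetidine to lactic acidosis; 2.5.2.3 ties reported cases to renal insufficiency. The exposure figures come from healthy volunteers, and the class label may already exclude cimetidine.

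The conclusion rests on the text of 2.5.2.5 and 5.3 alone. How often cimetidine is used is unknown and may be close to never. The criterion governs use at entry, so it would not reach cimetidine started after randomisation. Sample size, power, error rates and the analysis are untouched.

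**What to change.** In 5.3, name cimetidine and make the lead-in fit the list. For example, after the existing lead-in add: *or that competes with metformin for renal tubular secretion (cationic drugs: the ten already listed, and cimetidine)*. Both changes are needed, since naming cimetidine alone would leave it under a lead-in that 2.5.2.5 contradicts.

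This wording leaves the rest of the criterion as it is. Glyburide and furosemide stay under the existing lead-in. Nifedipine stays permitted: 2.5.2.5 reports a minimal effect of metformin on it and attributes its own effect to better absorption of metformin, so neither part of the lead-in reaches it. A broader phrase covering any drug that affects metformin should be avoided, because it could bring in nifedipine.

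The cost is one clause and one drug name. Drug history is already taken at recruitment (7.1.3), so no new data are needed. The only loss is current cimetidine users who would not already have been excluded under the class label, possibly very few.

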# Outcomes

## 6.1 Primary outcome

Prolongation of gestation measured from the time of enrolment to the time of delivery, in hours and days.

## 6.2 Secondary outcomes

### 6.2.1. Composite maternal outcome:

- The occurrence of any of the following serious maternal outcomes:
  - Maternal death
  - Eclampsia
  - Pulmonary oedema (oxygen saturation  $\leq 90\%$ , with clinical signs and symptoms requiring treatment)
  - Severe renal impairment or the need for dialysis
  - Cerebral vascular event
  - Liver haematoma or rupture
  - Placental abruption

### 6.2.2. Composite neonatal outcome:

- The occurrence of any of the following serious neonatal outcomes:
  - Neonatal death within 6 weeks after the due date
  - Grade III or IV intraventricular haemorrhage defined on imaging as enlarged ventricles associated with haemorrhage or when the haemorrhage extends into the cerebral tissue around the ventricles
  - Necrotizing enterocolitis diagnosed on radiographic studies
  - Bronchopulmonary dysplasia defined as needing oxygen at day 28 of life, either on a ventilator, by CPAP or via a nasal catheter
  - Significant neonatal sepsis as defined by the attending paediatrician.

## 6.3 Exploratory outcomes

### 6.3.1 Exploratory maternal outcomes

- Maternal death
- Eclampsia
- Pulmonary oedema (oxygen saturation  $\leq 90\%$ , with clinical signs and symptoms requiring treatment)
- Severe renal impairment or the need for dialysis
- Cerebral vascular event
- Liver haematoma or rupture
- Placental abruption
- Admission to a high care or intensive care unit
- Posterior reversible encephalopathy syndrome (diagnosed on imaging)
- Left ventricular failure (diagnosed on echocardiography)
- Serum creatinine greater than or equal to  $125 \mu\text{mol/l}$
- Proteinuria greater than or equal to  $3\text{g}/24\text{h}$
- Hypertension with a systolic blood pressure greater than  $160\text{mmHg}$  or a diastolic blood pressure greater than  $110\text{mmHg}$  despite anti-hypertensive treatment
- Disseminated intravascular coagulation
- Platelet count less than  $50 \times 10^9$
- Haemolysis, elevated liver enzymes and low platelets (HELLP) syndrome defined as a platelet count less than  $100 \times 10^9/\text{L}$ , aspartate aminotransferase greater than  $60 \mu/\text{L}$ , and haemolysis as demonstrated by lactate dehydrogenase greater than or equal to  $600 \mu/\text{L}$  or haemolysis on a peripheral blood smear or a raised haptoglobin level)
- Liver transaminases  $> 500\text{IU}/\text{L}$
- Placental abruption defined as a retroplacental clot covering more than 15% of the maternal surface or a diagnosis on histology
- Mode of delivery
- Use of antihypertensive agents (number of agents and daily dose at delivery)
- Major postpartum haemorrhage (defined as blood loss of more than 500mls at vaginal delivery and 1000 mls at caesarean section in the first 24 hours postpartum)
- Thromboembolic disease (defined as a deep-vein thrombosis, pulmonary embolism or both)
- Moderate or severe ascites noted on ultrasound or at delivery

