## **7.5 Sample collection**

### **7.5.1 Blood samples**

Blood samples are taken as part of routine clinical care (twice a week). These include measurements of the haemoglobin, the platelet count and the urea and creatinine levels. If HELLP syndrome is suspected the hepatocellular enzymes are measured and a coagulation profile may be ordered. We will collect an extra 9 mls of blood each time routine bloods are taken to obtain plasma samples. These will be processed immediately and frozen at -80°C for later analysis of sFlt1, sEng, and endothelin 1.

Tubes will be labelled with the participant's trial number and the date of collection. The samples will be spun and split into two aliquots. The aliquots will be stored in a minus 80-degree freezer and will be analysed at the end of the study.

We plan to measure the following in the blood samples:

- ***Biomarkers of endothelial injury:*** endothelin 1 and inflammatory cytokines
- ***Antiangiogenic factors associated with pre-eclampsia:*** sFlt1 and soluble endoglin
- ***Metformin levels in the blood in a subcohort cohort of patients:***

There is little data available on the pharmacokinetics of metformin in pre-eclampsia. We propose to perform pharmacokinetic testing on a subgroup to determine if there are differences in the pharmacokinetics of metformin in the pregnant pre-eclamptic population and to confirm that the levels found in preeclampsia are similar to the levels found in healthy controls.

Fifteen patients will undergo pharmacokinetic testing before the PI2 trial is started. They will all be given metformin and will not be included in the 150 participants for PI2. If consent is given, blood will be drawn from an indwelling catheter in a forearm vein at 5 minutes at the following dosing interval: ,2,4,6,7,8 and 24 hours after the initial dose is given. A further single sample will be drawn on day 5 with a butterfly needle. Each sample will be four milliliters. The total amount of blood taken will be 28 mls. Cord blood samples will also be obtained from the umbilical cord to determine the fetal exposure.

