## 8.6 Statistical methods

The patient characteristics at randomization, by treatment group, will be presented as mean (SD), median [25th – 75th percentile], minimum, maximum and count (%) depending upon type and distribution. The distribution of baseline characteristics between treatment groups will not be subject to hypothesis testing.

The primary outcome will be measured from the time of randomisation to delivery. Secondary maternal and neonatal outcomes will be measured from the time of recruitment until six weeks after the due date. The significance level for the primary outcome is set at 0.05 and all hypothesis testing will be two-sided. If, and only if, there is a significant difference for the primary outcome, the two secondary outcomes will be tested at a significance level of 0.025. Standard 95% confidence interval (CI) will be used to present the analysis of the primary outcome. The width of the CI used will be adjusted for the secondary outcomes if tested. For raw results data, the primary outcome will be summarized using median [25th – 75th percentile] along with minimum and maximum values.

All secondary outcomes and exploratory outcomes of interest will be presented by number (%) by treatment arm. Primary outcome effect size will be presented as difference in medians and 95% CI, adjusted for gestational age strata based upon the quantile regression model. P-values will be reported with associated with 95% CI for the secondary outcomes if tested. Exploratory outcomes will be presented with 95% CI.

Modelling will use quantile regression to assess difference in median prolongation between groups. This will be supplemented by survival analysis (i.e. time until delivery), using Cox proportional hazards regression (CPH) and Kaplan-Meier survivorship curves. Survival outcomes will not be subject to hypothesis testing. For both quantile regression and survival analysis effect estimates will be presented as group difference with 95% CI.

The number of events for each of the composite binary outcomes is likely to be small. An exact logistic regression model containing treatment group and gestational age strata will be used. In the event that it is not possible to obtain estimates, due to small counts each hypothesis will be tested, unadjusted for gestational strata, using Fisher's exact test. Point estimates of percentage and exact 95%CI will also be provided.

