Composite secondary outcome definitions:

(i) Maternal composite outcome: the occurrence of any of the following serious maternal outcomes: maternal death, eclampsia, pulmonary oedema (oxygen saturation $\leq 90\%$, with clinical symptoms requiring treatment), severe renal impairment or the need for dialysis, a cerebral vascular event, placental abruption and liver haematoma or rupture.

(ii) Neonatal composite outcome: the occurrence of any of the following serious neonatal outcomes: neonatal death within 6 weeks after the expected due date, grade III or IV intraventricular haemorrhage, necrotizing enterocolitis and bronchopulmonary dysplasia

Exploratory outcomes:

All other outcomes, including outcomes nested within individual secondary outcomes or outcomes with less clinical interest than secondary outcomes are classified as exploratory outcomes. These will not be subject to hypothesis testing, but precision of point estimates and may be presented using unadjusted 95%CI.

24. Statistical Analysis methods

Raw data primary outcome:

For raw results data, the primary outcome will be summarized using median [25th – 75th percentile] along with minimum and maximum values. All secondary outcomes and exploratory outcomes of interest will be presented by number (%) by treatment arm. Primary outcome effect size will be presented as difference in medians and 95%CI, adjusted for gestational age strata based upon the quantile regression model p-values will be reported associated with 95%CI for all testable outcomes.

Primary outcome:

Modelling will use quantile regression to assess difference in median prolongation between groups. This will be supplemented by survival analysis (i.e. time until delivery), using Cox proportional hazards regression (CPH) and Kaplan-Meier survivorship curves. Survival outcomes will not be subject to hypothesis testing. For both quantile regression and survival analysis effect estimates will be presented as group difference with 95% confidence intervals (95%CI).

Secondary outcomes:

The number of events for each of the composite binary outcomes is likely to be small. An exact logistic regression model containing treatment group and gestational age strata will be used. In the event that it is not possible to obtain estimates, due to small counts each hypothesis will be tested, unadjusted for gestational strata, using Fisher's exact test. Point estimates of percentage and exact 95%CI will also be provided.

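### The exploratory HELLP outcome takes a raised haptoglobin as evidence of haemolysis, which is the wrong direction, and it does not match the HELLP exclusion criterion

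*Protocol*

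**What the plan says.** Protocol 6.3.1 (Exploratory maternal outcomes) gives a three-part rule. The first part is "Haemolysis, elevated liver enzymes and low platelets (HELLP) syndrome defined as a platelet count less than" 100 × 10⁹/L. The second is "aspartate aminotransferase greater than" 60. The third is haemolysis, which can be shown in any of three ways: "and haemolysis as demonstrated by lactate dehydrogenase greater than or equal to" 600, or "haemolysis on a peripheral blood smear or a raised haptoglobin level". The three ways are joined by 'or', so any one of them satisfies the third part.

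Protocol 5.3 (Exclusion criteria) uses the same syndrome at presentation, with the same platelet and AST limits, but asks for "haemolysis as demonstrated by lactate dehydrogenase > 600 µ/L or haemolysis on a peripheral blood smear". Haptoglobin does not appear there, and the LDH boundary is strictly above 600 rather than 600 or above.

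On testing, 7.5.1 (Blood samples) says: "If HELLP syndrome is suspected the hepatocellular enzymes are measured and a coagulation profile may be ordered". It does not name haptoglobin, and neither does the routine surveillance in 7.3.1.

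On analysis, SAP section 23 says of exploratory outcomes: "These will not be subject to hypothesis testing". Protocol 8.6 says: "Exploratory outcomes will be presented with 95% CI", alongside number and percentage by arm.

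**The concern.** Haptoglobin binds free haemoglobin and is cleared with it, so haemolysis lowers the level. A raised value is not evidence of haemolysis. The documents do not state this direction themselves; it is elementary physiology. Nothing elsewhere in the protocol or SAP corrects the word or gives a cut-off.

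Two things follow. First, where haptoglobin is the deciding test, the rule gives the wrong answer for both abnormal results: it admits a woman whose result does not indicate haemolysis and passes over one whose result does. Second, the entry and outcome definitions of one syndrome differ, so the same blood results can fail to exclude a woman under 5.3 and yet score as an outcome under 6.3.1. Nothing in 6.3.1 says that HELLP must be first met after randomisation.

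What is at stake is the HELLP count reported by arm. HELLP is not a component of the maternal composite, so this line is the only place where the trial measures it as an outcome. Protocol 14.2 looks ahead to a larger trial better powered for maternal and neonatal outcomes, to which a faulty definition could be carried over.

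**Working it through.** The plan states no figure that depends on this definition, so there is none to reproduce. The check is to write out the rule and see which result patterns change.

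Inputs, all from Protocol 6.3.1 and 5.3: platelets (met or not), AST (met or not), LDH (met or not), smear (met or not), haptoglobin (raised, normal or low). That gives 2 × 2 × 2 × 2 × 3 = 48 patterns.

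Rules compared:

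- As written in 6.3.1: platelets AND AST AND (LDH OR smear OR raised haptoglobin).
- Direction reversed: platelets AND AST AND (LDH OR smear OR low haptoglobin).
- As in 5.3: platelets AND AST AND (LDH OR smear).

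Only patterns with both platelets and AST met can count: 2 × 2 × 3 = 12, or four for each haptoglobin result. Patterns counted as HELLP:

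| Haptoglobin | 6.3.1 as written | Direction reversed | 5.3 |
|---|---|---|---|
| Raised | 4 of 4 | 3 of 4 | 3 of 4 |
| Normal | 3 of 4 | 3 of 4 | 3 of 4 |
| Low | 3 of 4 | 4 of 4 | 3 of 4 |
| Total | 10 | 10 | 9 |

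Reversing the direction changes exactly two patterns. Both have platelets and AST met, LDH below 600 and no haemolysis on smear. With raised haptoglobin the pattern moves from counted to not counted; with low haptoglobin it moves from not counted to counted. The total stays at 10 because the two changes offset, although different women are labelled.

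One pattern separates 6.3.1 as written from 5.3: platelets and AST met, LDH and smear negative, haptoglobin raised. The table treats LDH as simply met or not. The difference between strictly above 600 and 600 or above adds one more discrepancy, at a value of exactly 600.

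These are counts of result patterns, not of women. The documents give no HELLP rate, no haptoglobin data and no frequency for any pattern, so the number of women affected cannot be calculated.

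**The case against.** The strongest reply is that this is a slip in one phrase with little reach, and most of that reply stands.

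- A reader might infer that a raised haptoglobin makes a woman a HELLP case, or that depleted haptoglobin is always missed. Neither follows. Platelets and AST must also qualify, and a woman with low haptoglobin is still counted if LDH or smear is positive.
- A reader might want to attach a percentage error to the HELLP count. The documents give nothing to base it on. Because haptoglobin is not a named test, it may decide no case at all.
- A reader might conclude that established HELLP is being counted as new on a notable scale. The LDH mismatch bites only at exactly 600. The haptoglobin route requires a woman with platelets below 100 × 10⁹/L and AST above 60 who was nevertheless judged suitable for expectant management. If raised haptoglobin is her only marker, haemolysis has not been shown, so she is a false positive rather than an established case.
- HELLP is not the only laboratory-scored outcome. Section 6.3.1 also lists creatinine, proteinuria, platelet count and transaminases.
- Failing to count a woman whose only marker is low haptoglobin is not in itself an error. The rule in 5.3 does the same, as would 6.3.1 with the limb deleted.

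What the reply does not remove is that the stated direction is wrong, that no other section corrects it, and that the two definitions of the same syndrome disagree.

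**Conclusion.** The point holds as a minor one. The haptoglobin limb in 6.3.1 is inverted, and misclassification is possible only when platelets and AST qualify, LDH and smear do not, and haptoglobin is either raised or low. The definition also differs from 5.3 in its haemolysis markers and in the LDH boundary, so a woman could meet the outcome on results that did not exclude her.

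The effect is confined to the reported HELLP count and may be small or nil. The primary outcome, the sample size, the significance level and the two composite secondary outcomes do not use this definition. HELLP has no row in the SAP draft tables. It would be wrong to infer any threat to the trial's main conclusions.

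The verdict rests on one fact from outside the documents, that haemolysis lowers haptoglobin. The disagreement between 5.3 and 6.3.1 can be seen from the text alone.

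**What to change.** In 6.3.1, either delete the haptoglobin limb or reverse it to a level below the laboratory's lower reference limit. Deletion is simpler: the pattern count becomes 9 of 48, the same as under 5.3. If the limb is kept, the limit needs to be written into the definition, and it will apply only to women who happen to have a haptoglobin result.

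Reconcile the LDH boundary and the haemolysis markers between 5.3 and 6.3.1. Which boundary to use is for the investigators to decide. The reconciliation should not add haptoglobin at entry, because that would alter an eligibility criterion and bring in a test that the protocol does not name.

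State in 6.3.1 that HELLP counts only when first met after randomisation.

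Cost: a short wording change to an outcome definition, applied when the data are coded and settled before unblinding. Deleting the limb needs no new tests. Treatment, sample size and the tested analyses do not change.
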